To investigate the long-term safety and tolerability of BRV in pediatric study participants with CAE or JAE	
TEAEs requiring a change in BRV doseMaximum intensity TEAE experienced (mild, moderate, and severe)Drug-related serious TEAEsFatal adverse events (AEs)TEAEs by maximum relationship (related and not related to BRV)SAEs by maximum relationship (related and not related to BRV) 
Occurrence of other seizure types, including generalized tonic-clonic seizures (GTCS), based on diary or EEG:
 
Non-absence seizures based on 1-hour EEGNon-absence seizures based on diary 
Estimand: the estimand is defined by the following 4 attributes that will be used to define the treatment effect of interest for the other safety analysis:
 
Population: population as defined in the protocol-specified inclusion/exclusion criteria reflecting the target patient population who receive at least 1 dose BRV during the study.Study participant-level outcome: occurrence of events in the list of endpoints above.Intercurrent event handling: the intercurrent event of concomitant medication use is handled by using a treatment policy strategy in which all AE/TEAE data or seizure data (as applicable) are included, regardless of receipt of any concomitant medication.Population-level summary measure: incidence rates. 
The intercurrent event of treatment discontinuation is handled by using a while-on-treatment strategy where observation ends at 14 days after treatment is stopped.

To investigate the long-term safety and tolerability of BRV in pediatric study participants with CAE or JAE	
CFB to each applicable visit in safety laboratory testsCFB to each applicable visit in electrocardiogram (ECG) parametersECG findings at each applicable visit

Table 2-1: Primary objective

Objectives	Endpoints/estimands
	
Physical and neurological examinations findings at each applicable visitPsychiatric and mental status at each applicable visitCFB to each applicable visit in vital signs (blood pressure, pulse rate, body temperature)CFB to each applicable visit in body weight and height

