3.3.3 Three- and six-month periods

A month is defined as 30 days and time intervals based on monthly durations are defined as a multiple of 30 days. The definitions of 3- and 6-month periods are described in [Table 3-3](#) and [Table 3-4](#) respectively.

Table 3-3: Definition of each 3-month period

Period	Days relative to date of first dose in EP0132
Months 1 to 3	1 to 90
Months 4 to 6	91 to 180
Months 7 to 9	181 to 270
Months 10 to 12	271 to 360
Months 13 to 15	361 to 450
Months 16 to 18	451 to 540
Months 19 to 21	541 to 630
Months 22 to 24	631 to 720
Months 25 to 27*	721 to 810
Months 28 to 30*	811 to 900
Months 31 to 33*	901 to 990
Months 34 to 36*	991 to 1080

Table 3-3: Definition of each 3-month period

Period	Days relative to date of first dose in EP0132
...	...

* These 3-month periods are only applicable for a subset of participants who remain in the EP0132 study past Month 24.

Table 3-4: Definition of each 6-month period

Period	Days relative to date of first dose in EP0132
Months 1 to 6	1 to 180
Months 7 to 12	181 to 360
Months 13 to 18	361 to 540
Months 19 to 24	541 to 720
Months 25 to 30*	721 to 900
Months 31 to 36*	901 to 1080
...	...

* These 6-month periods are only applicable for a subset of participants that remain in the EP0132 study past Month 24.

Three-month periods will be utilized for summaries and analyses of efficacy based on seizure data (diary data), AEs, and other safety endpoints. Six-month periods will be utilized for efficacy analyses of seizure data based on EEG, and consecutive and cumulative consecutive absence seizure freedom based on seizure data (EEG and diary data). For the analysis of AEs, participants will be included in 3-month period summaries if the end date of their Evaluation Period is on or after the first day of the 3-month period respectively.

Assessment visits are scheduled based on months calculated as 365.25/12 and thus are not fully aligned to the 3-month or 6-month periods described above. For example, the 7 to 12 month period would end at 360 days whereas the Month 12 visit is scheduled at 365 days. Similarly, the 19 to 24 month period would end at 720 days whereas the Month 24 visit is scheduled at 731 days. Further details are provided in [Table 3-5](#).

Table 3-5: Study periods vs scheduled assessments

Period	Days relative to date of first dose in EP0132	Scheduled assessment visit ^a	Scheduled assessment visit (days)
Months 1 to 3	1 to 90	MEV, Month 3	91

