3.13.4 Absence seizure freedom based on diary (including dropouts)

The endpoint of absence seizure freedom based on diary will be assessed at 3-month time intervals within the Evaluation Period, as defined in [Table 3-3](#), and over the entire Evaluation Period. The Evaluation Period may include any additional diary entries collected from the end of the Months 22 to 24 period up to the Month 24 YEV where the Evaluation Period is truncated for participants who reach the Month 24 YEV.

In each 3-month period (or Evaluation Period), a study participant is defined as absence seizure free if they meet all the following criteria:

1. The study participant completed their seizure diary on at least 80% of days within the relevant period. Seizure diary is defined as completed if “Diary completed” is answered “Yes” for each applicable day in the period. If “Diary completed” is answered “No” or the diary record is missing it will be defined as not completed for that day.
2. No absence seizures are reported in the seizure diaries in the relevant period
3. No concomitant use of any AEDs, including benzodiazepines during the relevant period

Specific algorithmic rules for each of the above criteria are defined as follows:

Criterion 1: Seizure diary data is reported on the Seizure Classification eCRF for at least 80% of the days within the relevant period

Criterion 2: No diary records on the Seizure Classification eCRF within the relevant period are reported with answer “Yes” to the question “Did Any Absence Seizures occur?”

Criterion 3: No records of any concomitant AED, including benzodiazepines, usage on the Concomitant Medications eCRF within the relevant period

Note that Criterion 2 and 3 will only be assessed if Criterion 1 is met. In each 3-month period (or Evaluation Period), if the study participant does not meet all the criteria for absence seizure freedom they will be regarded as not absence seizure free.

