3.13.8 Consecutive absence seizure freedom based on EEG

The endpoint of consecutive absence seizure freedom based on EEG is defined per 6-month period as having no absence seizures on scheduled or unscheduled EEGs during that period.

The endpoint of cumulative consecutive absence seizure freedom based on EEG is defined per 6-month period as having no absence seizures on scheduled or unscheduled EEGs during that period and all preceding periods.

Consecutive absence seizure freedom based on 1-hour EEG will be assessed at each FEV, YEV, and FV, as applicable, individually and cumulatively at each visit, truncated at the Month 24 YEV (for participants who reach Month 24). The derivation will be the same as that outlined in [Section 3.13.2](#), except without the consideration of concomitant AEDs or benzodiazepines usage. In addition, for this analysis, unscheduled EEGs and EEGs performed at the EDV that were not mapped to a scheduled visit will be considered.

In each 6-month period, a study participant is defined as absence seizure free if they meet all the following criteria:

1. At least one 1-hour EEG (either scheduled or unscheduled) was conducted on the study participant at any time up to and including the scheduled FEV or YEV at the end of the 6-month period
2. Quality of at least one 1-hour EEG while awake deemed sufficient for analysis
3. No absence seizure identified while awake on any 1-hour EEG (scheduled and unscheduled) performed within the specified period

Specific algorithmic rules for each of the above criteria are defined as follows:

Criterion 1: A study participant is defined as receiving the 1-hour EEG if there is a record in the eCRF that at least one 1-hour EEG was conducted (either scheduled or unscheduled) within the 6-month period.

Criterion 2: The EEG is deemed of sufficient quality if at least 30 minutes of readable EEG while awake is recorded for at least one 1-hour EEG during the specified 6-month period. Note that if a participant has more than one 1-hour EEG during a 6-month period, it is only necessary to meet this criterion for one of these assessments.

Criterion 3: 1-hour EEG with no absence seizures recorded on the EEG eCRF (ILAE code IIA). Note that Criterion 3 must be met for all EEGs performed within the specified 6-month period regardless of whether each of these EEGs fulfils Criterion 2.

Note that Criterion 2 and 3 can only be assessed if Criterion 1 is met.

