8.1.4 Absence seizure freedom based on diary (excluding dropouts)

The number and percentage of study participants who are absence seizure free based on diary will be summarized at 3-month time intervals within the Evaluation Period, as defined in [Table 3-3](#), and over the entire Evaluation Period truncated at the scheduled Month 24 YEV for participants who continue in the study beyond 2 years. The latter will additionally include any diary entries collected from the end of the 3-month period Months 22 to 24 up to the Month 24 YEV. The derivation of absence seizure freedom based on diary is specified in [Section 3.13.5](#). The number and percentage of study participants who met each individual criterion will be summarized, irrespective of whether the other criteria were met.

If a study participant discontinues the study during a 3-month period and does not meet Criterion 1 (as defined in [Section 3.13.4](#)) during the period of study discontinuation, the participant will be excluded from this period and all subsequent periods. If a study participant discontinues the study at any time before the Month 24 YEV, they will not be included in the analysis conducted on the Evaluation Period.

The denominator for the percentages of participants that met Criterion 1 will be based on the number of participants with data in the SS. The denominator for all other percentages for each 3-month period will be based on the number of participants who met Criterion 1 during the period. Similarly, the denominator for percentages for the analysis on the Evaluation Period (truncated at Month 24 YEV) will be the number of participants who did not discontinue the study prior to the Month 24 YEV (or FV).

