10.5.1 Non-absence seizure incidence during the study based on locally read 1-hour EEGs

The incidence of each non-absence seizure type will be summarized over the entire Evaluation Period (including unscheduled visits and visits beyond Month 24) and by visit. Summaries by visit will also include scheduled assessment timepoints beyond Month 24, with scheduled assessment timepoints beyond Month 24 included if at least one participant has an assessment at the timepoint. Study participants who experience more than one non-absence seizure type during a visit (ie, POS and tonic-clonic, POS and other seizure, tonic-clonic and other seizure or all three seizure types) will be counted once for each non-absence seizure type. Percentages for the by visit summary will be relative to the number of participants with a 1-hour EEG at the visit with at least 30 minutes of readable EEG time while awake. Percentages for the Evaluation Period will be relative to the number of participants with at least one (scheduled or unscheduled) 1-hour EEG with at least 30 minutes of readable EEG time while awake occurring on or after the first dose of study treatment in EP0132.

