10.5.2 Non-absence seizure incidence during the study based on seizure diary

The incidence of each non-absence seizures type observed from the seizure diary will be summarized over the entire Evaluation Period (including unscheduled visits and visits beyond Month 24) and by 3-month period, as defined in [Table 3-3](#); 3-month periods from and beyond Months 25-27 will be included if at least one participant has started the relevant 3-month period. Study participants who experience more than one non-absence seizure type during a 3-month period (ie, POS and tonic-clonic, POS and other seizure, tonic-clonic and other seizure or all three seizure types) will be counted once for each non-absence seizure type. Percentages for the

each 3-month period will be relative to the number of participants who completed their seizure diary on at least 80% of days within the 3-month period. Percentages for the Evaluation Period will be relative to the number of participants who completed their seizure diary on at least 80% of days over the Evaluation Period.

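### Read naturally, SAP 10.5.1 and 10.5.2 leave non-absence seizures recorded below the awake-EEG or diary threshold out of the summary tables; one Safety Set row per seizure type would keep them (minor)

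*SAP*

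**What the plan says.** Non-absence seizures, on the 1-hour EEG and in the diary, are among the other endpoints of the primary safety objective (Protocol Section 3; SAP Table 2-1). SAP 2.2.1 describes the estimand population as "reflecting the target patient population who receive at least 1 dose BRV during the study". It sets no condition on diary completion or EEG duration.

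SAP 10.5.1 summarises each seizure type by visit and over the Evaluation Period. By-visit percentages are "relative to the number of participants with a 1-hour EEG at the visit with at least 30 minutes of readable EEG time while awake". For the Evaluation Period, one such recording, scheduled or unscheduled, is enough to enter the base.

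SAP 10.5.2 does the same for the diary. Percentages for "each 3-month period will be relative to the number of participants who completed their seizure diary on at least 80% of days within" that period, and the Evaluation Period row applies the 80% rule to the whole of that period.

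Both sections describe the numerator only as the incidence of each type, with a participant counted once per type. Protocol 7.3.1 and 8.1.10.1 and SAP 2.3.3.1 have sleep as well as wakefulness read for non-absence seizures, but only awake minutes count towards the 30.

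**The concern.** A completeness threshold makes sense when the claim is that no seizure occurred, because a thin record cannot support that claim. It fits less well when the table counts harms, because a recorded seizure is known to have happened however sparse the rest of the record is.

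A tonic-clonic seizure entered in a diary just under 80% complete, or seen on a mostly asleep EEG with fewer than 30 awake minutes, is a known event in a treated participant. If the numerator is confined to those above the threshold, that participant does not appear in the table. If it is not confined, the participant appears on top of the fraction but not underneath it. The text does not say which applies. Protocol 2.3 describes tonic-clonic seizures as common in JAE, so the category will not necessarily be empty.

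**Working it through.** **Figure to reproduce.** None. The plan states no expected seizure rate, diary-completion rate or sample size calculation.

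**Is the numerator defined elsewhere?** No. SAP 3.13.1.1 defines seizure types only. SAP 3.2 gives a default denominator, which 10.5 replaces. Protocol 9.4.1 promises a descriptive summary without naming a base. Table 2-1 addresses concomitant medication and treatment discontinuation, not completeness.

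**Inputs.** N = 140, the approximate enrolment in Protocol 9.8 and SAP 2.4, taken here as the Safety Set. Everything else is assumed: E = 10 participants with a given seizure type; n = 14, 28 or 42 below the threshold (f = n/N = 10%, 20%, 30%); e = how many of the 10 are below it.

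**Reference.** All recorded events over all participants: E/N = 10/140 = 7.1%.

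**Literal reading (all events kept, restricted base).** Percentage = E/(N − n) = (E/N) × 1/(1 − f).

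| f | N − n | Percentage | Factor |
|---|---|---|---|
| 10% | 126 | 10/126 = 7.9% | 140/126 = 1.11 |
| 20% | 112 | 10/112 = 8.9% | 140/112 = 1.25 |
| 30% | 98 | 10/98 = 10.2% | 140/98 = 1.43 |

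**Natural reading (events below the threshold dropped).** Percentage = (E − e)/(N − n). At n = 28:

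| e | Percentage |
|---|---|
| 0 | 10/112 = 8.9% |
| 1 | 9/112 = 8.0% |
| 2 | 8/112 = 7.1% |
| 4 | 6/112 = 5.4% |

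The result equals the reference when e/E = n/N, here 2/10 = 28/140. It lies above the reference when recorded events are rarer below the threshold and under it when they are more frequent, so the direction is not fixed.

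**Who falls below 80%.** 0.80 × 90 = 72 days. If 80% is judged on the full 90-day period, as SAP 3.13.4 does for leavers, a participant who leaves on days 1 to 71 is below the threshold for that period even with a perfect diary (71/90 = 78.9%). SAP 10.5.2 does not state its basis. The Evaluation Period row is not affected in this way, because that period ends at the participant's own final or early discontinuation visit (SAP Table 3-2).

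**The case against.** The strongest reply is that a percentage relative to a set of participants is ordinarily computed within that set. The literal reading can even produce impossible results: if 5 participants started a late period, 2 passed the threshold and 3 had the event (all assumed), it gives 3/2 = 150%. The restricted base also avoids counting people with sparse records as event-free. The 30-minute rule is the protocol's own evaluability rule (Protocol 7.3.1), so using it is no departure. Nothing is tested, and SAP Section 8 lists the EEG and diary data in full. All of this stands. It makes the inflation factors the less likely branch, and it makes the numerator wording a clarification.

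Four stronger readings may tempt a reader; the documents do not support them.

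- **That the SAP elsewhere uses unmatched numerators.** SAP 8.1.4 counts participants "who met each individual criterion will be summarized, irrespective of whether the other criteria were met", while its "denominator for all other percentages for each 3-month period will be based on the number of participants who met Criterion 1". But its derivation runs through 3.13.5 to 3.13.4, which says: "Note that Criterion 2 and 3 will only be assessed if Criterion 1 is met". Nobody below 80% can enter those counts.
- **That 3.13.8 sets a conflicting precedent.** There, the no-seizure criterion "must be met for all EEGs performed within the specified 6-month period regardless of whether each of these EEGs fulfils Criterion 2". In that analysis a seizure defeats a responder status, and the seizure-freedom percentages use the Safety Set. There is no restricted base to mismatch.
- **That the adverse event tables show an inconsistency.** For those, "participants will be included in 3-month period summaries if the end date of their Evaluation Period is on or after the first day" of the period. Adverse events are not collected by daily diary, so a completion threshold would have no meaning for them.
- **That the adverse event tables will miss these seizures.** Protocol Appendix 3 excludes expected signs of the disease unless more severe than expected. It also makes exacerbation in frequency or intensity an adverse event, and it names convulsions without hospitalisation as a possible important medical event. Table 8-2 anticipates convulsion and status epilepticus as serious events that must still be reported, and the investigator confirms adverse events when reviewing the diary (Protocol 7.3.2). Worsening or serious seizures therefore have another route. Expected, non-worsening ones may not.

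**Conclusion.** The concern holds as a minor point, worth considering. As naturally read, the two tables omit recorded non-absence seizures in participants below the threshold, although the estimand they serve includes every treated participant and sleep is read for these events. The size cannot be stated from the documents. With assumed shares of 10% to 30% below the threshold, the less likely literal reading inflates the percentage 1.11 to 1.43 times. Under the natural reading, the assumed example runs from 5.4% to 8.9% against 7.1% over all participants.

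The all-participant figure is a reference and not the truth, since it treats unobserved time as event-free. A known bias in either direction should therefore not be inferred. The effect is confined to summary tables: the listings keep the data, and the adverse event and serious adverse event routes catch part of what the tables leave out.

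**What to change.** 1. Keep the present percentages in SAP 10.5.1 and 10.5.2, and state that the numerator is limited to the same participants as the denominator.
2. Add one row per seizure type to each table: the number and percentage of Safety Set participants with any recorded non-absence seizure of that type, awake or asleep, whatever the diary completion or awake EEG time. For a 3-month period, use those who entered it; SAP 3.3.3 already has a workable entry rule. Print beside it the number with any diary day or any 1-hour EEG performed.
3. As a clarification only, say in 10.5.2 whether the 80% is taken over the full 90 days or over days in the study.

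The main denominators do not change. The cost is a few sentences of SAP text and one table row per seizure type, with no new data. The downside is that participants with sparse diaries or short awake time and no recorded event count as event-free in the added row. The existing row beside it and the printed counts let the reader see how far that matters.

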10.6 Participant and caregiver-reported outcomes

10.6.1 EpiTrack Junior

The absolute values and CFB in the EpiTrack score will be summarized at each visit using descriptive statistics.

In addition, the number and percentage of study participants in the following categories at each visit will be provided for the SS:

- Cognitive performance categories (good, average, mildly impaired, or significantly impaired) at each scheduled visit. Percentages will be relative to the number of study participants with a measurement at the visit.
- Significant change categories of cognitive function (improved, unchanged, worsened) for each visit compared to N01269 Baseline. Percentages will be relative to the number of study participants with a non-missing CFB at the visit.

All available data related to each sub-test result and associated scores, the total unadjusted score, and the Epitrack score will be listed by visit. Study participants who turn age 6 years after N01269 Baseline will be excluded from all summaries, but their results will be included in listings. Study participants who turn age 18 prior to or on the first scheduled assessment in EP0132, which is planned at Month 6, will also be excluded from all summaries, but their results will be included in listings.

10.6.2 PedsQL

The absolute and CFB in total PedsQL score, Physical Health Summary Score, Psychosocial Health Summary Score, and Emotional, Social and School Functioning dimension score will be summarized using descriptive statistics. The Physical Functioning dimension will not be summarized as it is the same as the Physical Health Summary Score.

Summaries of the participant self-report will be reported over all age groups and separately for Young Children (ages 5 to 7), Children (ages 8 to 12) and Teens (ages 13-18), based on the participants age at N01269 Baseline. The summary over all age groups will exclude participants aged 2 to 4 years old since only a parent proxy report is available for this age group.

Similarly, summaries of the parent proxy report will be reported for all age groups and separately for Toddlers (ages 2 to 4), Young Children (ages 5 to 7), Children (ages 8 to 12) and Teens (ages 13-18). The summary over all age groups will exclude the 2 to 4 years age group as it includes fewer items. The summary for 2 to 4 years age group will include the absolute and CFB score only until the participant turns 5 years old (as CFB are not calculated for subsequent versions of the questionnaire for this age group).

The number and percentage of participants with meaningful changes in PedsQL score from N01269 Baseline will be presented at each visit. This will be presented separately for the participant self-report and the parent proxy report. Each dimension score (total scale score, physical health summary score, psychosocial health summary score, emotional functioning,

social functioning and school functioning) will be presented and the summary will be aggregated over all age groups. However, the summary will exclude the parent proxy report for participants 2-4 years' age group. The denominator for percentages will be the number of participants with a non-missing CFB score at the visit.

In addition, all available data for the PedsQL will be listed.

